### **Procedures**

**Pre-implementation Phase** (5 months). Recruitment will begin and we will identify a physician "champion" and an office staff member to lead implementation in each practice. Practices will choose by month 4 SEEKonline or the Traditional paper and pencil approach. To ease introduction of the SEEK model, we will address logistical issues such as for which checkups parents will complete the SEEK PQ and documentation in the EHR. SEEK Parent Handouts will be customized with information on local resources and PCPs will complete the SEEK Primary Care Provider Questionnaire (PCPQ) prior to the SEEK training.

**Implementation Phase.** In month 5, practices in cohort 1 will be randomized to one of the two SEEK training strategies (MOC or IND), stratified by practice type (pediatric or family medicine). At the end of training in month 8, PCPs will evaluate it. After the training, PCPs will be asked to participate in 3 webinars

every 4 months to discuss implementation and clinical issues. By month 8, interested practices will have SEEKonline connected to their EHR, ensuring interoperability. In month 9, the SEEK intervention will begin in cohort 1. Practice leaders, PCPs, behavioral health professionals and office staff will be asked to complete the online SEEK Adoption Survey, regardless of full participation. Parents also will begin completing surveys. Purposive subsamples from each group will be selected for 30-minute phone qualitative interviews. The process for cohort 2 will begin in month 11 and the SEEK intervention will start in month 16. Procedures are detailed under Human Subjects for addressing concerns of possible child abuse or neglect.

**Sustainment Phase.** Participants will be assessed at 12, 21 and 33 months post baseline regarding their thinking, feeling, behavior and experiences (see Table 3) to help inform understanding of SEEK's implementation and sustainment. At months 41 and 48, the observation period will end for cohorts 1 and 2. Final surveys and phone interviews will assess participants' thoughts and plans about continued use of SEEK. Following the grant period, practices that wish to continue utilizing the implementation strategies will be guided through the process of establishing real-world, not-grant funded contracting.

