### **Organizational Assessment**

Organizational measures will be administered at baseline regarding the opportunity to adopt SEEK. Practice leaders and PCPs who decide to participate in the study will be recruited; those who opt out will be asked to complete the one-time brief online SEEK Adoption Survey and the following 4 measures. A subsample will undergo a semi-structured, 30-minute phone interview.

**Demographics Form.** This includes the healthcare system and practice structure, annual budget, number of practices, number and characteristics of PCPs, presence of behavioral health and patient demographics.

**Evidence-Based Practice Attitude Scales (EBPAS).** The 15-item EBPAS measures 4 domains of service providers' attitudes toward adopting EBPs: *appeal* (the extent to which one would adopt an EBP if it is appealing), *requirements* (willingness to adopt an EBP if required to do so), *openness* (general openness to new interventions), and *divergence* (the degree to which one believes that EBPs are less important than clinical experience). Subscales have adequate internal consistency (Cronbach's  $\alpha = .67\text{-.91}$ ) and convergent validity.

**Implementation Leadership Scale (ILS).** The 12-item ILS assesses leader support for EBPs within an organization (5-point Likert scale). Four subscales - *proactive*, *knowledgeable*, *supportive*, and *perseverant* leadership - have excellent internal consistency ( $\alpha = .95$  to  $.96$ ), and convergent and discriminant validity.

**Implementation Climate Scale (ICS).** The 18-item ICS assesses how the organization views new interventions. Implementation climate is defined as shared perceptions of policies, practices, procedures and behaviors that are rewarded, expected and supported. The measure has strong psychometrics with internal consistency ( $\alpha = .81\text{-.91}$ ), convergent validity, and validation in a sample of child welfare professionals.

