**Table 3: Study Measures Related to Specific Aims**

Domain/Measure	Aims	Respondent*	Baseline** A: mo 8 B: mo 15	Training A: by mo 9 B: by mo 10	F/U 1 A: mo 20 B: mo 27	F/U 2 A: mo 29 B: mo 30	F/U 3 A: mo 41 B: mo 48
Organizational							
System Demographics	1, 2, 3	SL	●			●	
Evidence Based Practice Attitude Scale	1, 2, 3	All, except parents	●		●	●	●
Implementation Leadership Scale	1, 2, 3	All, except parents	●		●	●	●
Implementation Climate	1, 2, 3	All, except parents	●		●	●	
Implementation Process							
Stages of Implementation	2, 3	AS	●	●	●	●	●
Adoption							
SEEK Adoption Survey	2, 3	SL, PL, PCP	●				
Seek Training							
SEEK Training Evaluation	1, 2, 3	PCP		●			
Child Maltreatment							
EHR review****		IT			●		●
Implementation Outcomes							
SEEK PCP Questionnaire	1, 2, 3	PCP	●	●	●	●	●
SEEK PCP Survey	1, 2, 3	PCP		●	●	●	●
SEEK Office Staff	1, 2, 3	AS		●	●	●	●
SEEK Parent View	1, 2, 3	P		●	●	●	●
Rate of Screening	1, 2, 3	EHR	●	●	●	●	●
Receipt of Services	1, 2, 3	EHR	●	●	●	●	●
Costs							
Cost of Implementing New Strategies (COINS)	2, 3	PL, AS, PCP			●	●	●
General							
Qualitative Phone Interviews	1, 2, 3	All		●	●	●	●

\*SL = system leaders, PL = practice leaders, PCP = primary care providers, BHP = behavioral health professionals, AS=ancillary staff, P=parents, BHP=behavioral health professional, IT=information technology

\*\*A = 1st cohort of healthcare systems and practices, B = 2nd cohort of healthcare systems and practices

\*\*\*\*Brief Child Abuse Potential Inventory, \*\*\*\*EHRs will be reviewed by IT toward end of study

Proportion Scores are calculated separately for each stage. The total Proportion Score is based on the number of activities completed out of the number that could be completed – for each stage.

Finally, the SIC Stage Score marks the final stage that a site reaches. SIC scores are calculated within each of the three Implementation Phases: Pre-implementation (stages 1-3), Implementation (stages 4-7), and Sustainment (stage 8).

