**Aim 2. Examine variations in SEEK's implementation process and impacts and understand associated barriers and facilitators in pediatric and family medicine practices.** We will determine the proportion of practices that agree to adopt SEEK. We will then quantitatively assess the relationship between practice characteristics (e.g., demographics, EBP attitudes) and willingness to adopt SEEK. The most important independent predictors will be determined using multivariable logistic regression models. Among those that do adopt SEEK, we will assess their degree of completeness, speed, and quality of implementation using the SIC. Completeness will be summarized using the final stage attained (0-8). Speed will be summarized by the duration in each stage, and quality by the proportion of activities performed at each stage, and overall. The distribution of these variables will be determined, overall and separately, based on the type of

practice. The distribution of time to achieve each phase will be estimated using the Kaplan-Meier approach. Barriers and facilitators to implementing SEEK will be probed quantitatively and qualitatively (see below). Among practices adopting SEEK, we will examine the association between practice characteristics and measures of completeness, speed, and quality of implementation from the SIC. We will examine relationships between practice characteristics and implementation by comparing the distribution of SIC scores in groups defined by practice characteristics. Finally, the most important predictors of degree of implementation will be determined using multivariable regression models with practice characteristics as predictors and SIC measures as outcomes. In addition to studying implementation at the practice level, we will analyze the relationship between PCP level measures of implementation (e.g., screening rates) and PCP characteristics, facilitators and barriers. These models will account for clustering of PCPs within practices, as described above.

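### The plan conflicts on whether Baseline precedes training; on the Table 3 calendar, Aim 2 could report a consequence of adopting SEEK as a predictor of adopting it

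*Combined protocol and SAP*

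**What the plan says.** Data Analysis Plan, Aim 2: the investigators will "assess the relationship between practice characteristics (e.g., demographics, EBP attitudes) and willingness to adopt SEEK", then pick out the main independent predictors by multivariable logistic regression. Nothing limits the model to scores taken before the decision or before training.

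Organizational Assessment: the organizational measures are given at baseline, in connection with the chance to adopt SEEK; no month is stated. For practice leaders and PCPs who decline, "those who opt out will be asked to complete the one-time brief online SEEK Adoption Survey and the following 4 measures". Those four are demographics, the EBPAS, the Implementation Leadership Scale (ILS) and the Implementation Climate Scale (ICS).

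Table 3, which the Timeline names as the data-collection calendar: the column headed "Baseline A: mo 8 B: mo 15" holds the EBPAS, the ILS, the ICS, the PCP Questionnaire (PCPQ) and the row "SEEK Adoption Survey". The next column is headed "Training A: by mo 9 B: by mo 10".

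Procedures: cohort 1 is randomised to a training strategy in month 5, and "At the end of training in month 8, PCPs will evaluate it". After the sentence on the month-9 launch, the text says of leaders, PCPs, behavioral health professionals and office staff that "office staff will be asked to complete the online SEEK Adoption Survey, regardless of full participation". The PCPQ, by contrast, is placed in the pre-implementation phase, ahead of training.

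**The concern.** A predictor of adoption has to be measured before adoption can change it. If joiners report their attitudes after signing up and being trained, while decliners answer without either experience, a higher EBPAS score among joiners may result from commitment and training. The model cannot separate that from a pre-existing attitude that led to adoption. Aim 2 might then name a product of adoption as a facilitator of it. This cannot be repaired at analysis, because joiners' scores at the decision would never have been recorded.

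The same concern applies to the ILS and ICS if they enter the model. It does not apply to demographics. For the Adoption Survey, which asks about reasons for the decision, the issue is retrospective recall.

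**Working it through.** The question is one of dates, so the check is calendar arithmetic followed by a comparison of sections.

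**1. Is month 8 a stray figure?** Procedures sets follow-ups at 12, 21 and 33 months after baseline. Implied baseline = follow-up month in Table 3 minus offset.
- Cohort 1: 20 − 12 = 8; 29 − 21 = 8; 41 − 33 = 8.
- Cohort 2: 27 − 12 = 15; 48 − 33 = 15; but 30 − 21 = 9 (month 36 would be expected, since 15 + 21 = 36).

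Month 8 is confirmed by all three cohort 1 follow-ups, and month 15 by two of three in cohort 2. The staff and parent interviews, set at 11, 20 and 32 months after launch, give the same cohort 1 months: 9 + 11 = 20, 9 + 20 = 29, 9 + 32 = 41. The calendar is built around month 8.

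**2. Where does that date fall relative to training?**
- Cohort 1: randomisation in month 5, training ends in month 8. Baseline is 8 − 5 = 3 months after randomisation, in the month training ends. It is 8 − 4 = 4 months after the deadline for choosing a delivery mode (month 4). If the Adoption Survey goes out at launch, it is 9 − 5 = 4 months after randomisation.
- Cohort 2: the Timeline repeats the recruitment-to-training process in months 11–15, so month 15 is the last month of that window. Table 3's training date for this cohort, month 10, precedes the month-11 start and settles nothing.

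**3. What points the other way?**
- Organizational Assessment links these measures to the opportunity to adopt, which reads naturally as the time of the decision.
- The PCPQ shares the Baseline column but is explicitly pre-training. Month 8 therefore cannot be the true date of every instrument in that column if training ends in month 8.
- In Table 3 taken alone, cohort 1 Baseline (month 8) comes before Training (by month 9).

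Steps 2 and 3 cannot both hold for the EBPAS, and no section says which governs.

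**4. Who answers?** Table 3 gives the EBPAS, ILS and ICS to everyone except parents; opt-out data are sought only from practice leaders and PCPs. For the Adoption Survey, Table 3 lists system leaders, practice leaders and PCPs, whereas Procedures omits system leaders and adds behavioral health and office staff. Practice-level scores could therefore average different roles in the two groups.

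**5. Can the bias be sized?** Not from the documents. As an assumption-only illustration, suppose 48 of the 59 practices join and the other 11 decline, all respond, there is no true difference at the decision, and commitment plus training lifts joiners' practice-level scores by d standard deviations. Then SE = √(1/48 + 1/11) = 0.334, and the chance of a significant association in the joiners' favour is about Φ(d/0.334 − 1.96).
- d = 0.2: Φ(0.598 − 1.96) = Φ(−1.36) ≈ 0.09.
- d = 0.5: Φ(1.496 − 1.96) = Φ(−0.46) ≈ 0.32.

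The nominal two-sided rate is 0.05. The values of d are not in the documents; the range shows only that a modest shift would matter.

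**The case against.** The strongest reply is that baseline ordinarily means before training and that the plan uses it so elsewhere: the Aim 1 example model contrasts baseline with a post-training measure, the PCPQ is placed before training, and Organizational Assessment speaks of the opportunity to adopt. On that reading month 8 is a loose column label and joiners and opt-outs are measured alike. This is a fair reading, and it stands to the extent that post-training measurement is not established. It does not remove the conflict, because staff told to use Table 3 for timing would field the scales in month 8.

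Four stronger readings are tempting and are not supported.
- A reader might infer that joiners certainly answer after months of training. The timing is unresolved. Moreover, only the MOC strategy runs over four months; the independent strategy is 2–3 hours of video and a post-test, and some EBPAS respondents are not PCPs and may receive no training.
- A reader might treat Adoption Survey answers as biased regression predictors. The Aim 2 model does not name them, and the survey sentence in Procedures carries no month of its own.
- A reader might assume that SEEK training raises EBPAS scores. The scale measures general attitudes to evidence-based practice, and no section gives an effect of training on it.
- A reader might extend the problem to Aim 1. The PCPQ is explicitly pre-training, so the randomised comparison is not implicated.

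The stakes are also bounded: Aim 2 has no numbered hypothesis, and its one entry in Table 4, the precision of the adoption rate, is unaffected.

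**Conclusion.** The point holds as a conflict that must be reconciled, with a conditional risk of bias. Table 3 and Procedures together put joiners' EBPAS, ILS and ICS after commitment and at about the end of training; Organizational Assessment and the placing of the PCPQ suggest collection beforehand. If the Table 3 calendar is followed, the Aim 2 model of willingness to adopt is open to reverse causation through the EBPAS (and the ILS and ICS if used), and the Adoption Survey to retrospective recall. The direction and size of the bias are unknown.

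The conclusion assumes that opt-outs are untrained, which is a reasonable inference although neither that nor the month of their single assessment is stated. It should be settled before the instruments are fielded. Aim 1's randomised comparison and Aim 3 are not affected.

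**What to change.** 1. Reconcile Procedures, Organizational Assessment and Table 3 so that joining and opting-out practices complete the EBPAS, ILS, ICS and Adoption Survey at the adoption decision, before randomisation and training (for cohort 1, before the month-5 randomisation).
2. Use the same respondent roles, practice leaders and PCPs, on both sides of the adoption comparison. Other staff may still answer for other purposes.
3. State in the Aim 2 analysis that the adoption model uses only these decision-time scores.
4. Keep the follow-up calendar months and restate their offsets. Counting 12, 21 and 33 months from an earlier cohort 1 baseline at month 4 or 5 would move follow-up to months 16–17, 25–26 and 37–38. Anchoring to launch instead (11, 20 and 32 months) keeps 20, 29 and 41. In the same edit, check Table 3's cohort 2 entries for training (month 10) and second follow-up (month 30), which do not fit the rest of the schedule.

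The cost is one online survey sent earlier to joiners and a reworded follow-up offset. No instrument is added, and consent, already taken online at the first survey, moves with it.

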**Training.** Two training strategies will be tested (see Table 1), both increasingly used with PCPs, and developed in accordance with principles of adult learning. First, *SEEK Maintenance of Certification (MOC-4)* is an example of a structured Quality Improvement (QI) project approved by the American Boards of Pediatrics and of Family Medicine, required of physicians to maintain Board certification. It includes viewing the training videos and implementing SEEK in one's practice and conducting the QI Plan-Do-Study-Act cycle. This PDSA cycle involves learning from data collected before and during SEEK's implementation to assess and improve the process. Four one-hour webinars over 4 months enable collaborative learning and mentoring. Second, Independent online (IND) training is a student-centered approach; it involves viewing the training videos over 2-3 hours and passing the post-test. Both approaches include three 1-hour consultations in the ensuing year and offer CME credits toward state licensure. Although both are convenient, we hypothesize that the interactive MOC-4 training will lead to more efficient and competent adoption of SEEK.

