### **Timeline** (See Table 3 for timing of data collection)

Month 1-8: Hire and train project coordinator and research assistant. Randomly select first 2 healthcare systems (one pediatric, one family medicine). Recruit practices and randomly assign to SEEK training strategies; complete training. Practices select SEEKonline or Traditional strategy, SEEKonline connected to practices' EHRs, computerize study protocol, obtain IRB approvals

Month 5-48: Periodic webinars with PCPs and evaluation of participants, develop papers and presentations

Month 9: Begin implementing SEEK model in cohort 1 of healthcare systems and practices

Month 11-15: Repeat above process with cohort 2 of healthcare systems and practices

Month 16: Begin implementing SEEK model in cohort 2

Month 46-48: End of observation period, practices decide whether to continue using SEEK, final surveys

Month 49-60: Data will be obtained from practices' EHRs re. implementation (e.g., rate of screening, CM-related ICD-10 codes), final data analyses, prepare Final Report and papers

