### **Qualitative Assessment: Phone Interviews**

To assess feasibility and acceptability and potential barriers and facilitators of the SEEK intervention, we will conduct 30-minute semi-structured phone interviews with purposively selected (based on role, practice type, training strategy and presence of behavioral health) subsamples of 5 groups: practice leaders, PCPs, behavioral health professionals, office staff and parents, at 3 time points. For the first 3 groups, these will be around the start of the intervention (probing adoption) and 11 and 21 months later. For the last 2 groups, interviews will be at 11, 20 and 32 months following start of the intervention, after they have experienced SEEK. Interviewers will

use a semi-structured guide similar to one previously employed. Participants will be asked about their experiences with SEEK, assessment of training and implementation support, challenges in delivering the intervention and recommendations for addressing the challenges. Interviews will be conducted by telephone and will be digitally recorded and professionally transcribed for analysis.

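### Table 3 dates the baseline PCPQ at the end of training (month 8 for cohort A, month 15 for cohort B), while Procedures requires it before training and the Aim 1 model relies on that

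*Combined protocol and SAP*

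**What the plan says.** The Timeline refers the reader to Table 3 for when data are collected. Table 3 heads its baseline column month 8 for cohort A and month 15 for cohort B (cohorts 1 and 2 in the text). It marks the PCPQ in that column, in the training column and at every follow-up.

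Procedures orders events differently. Under the pre-implementation phase, "PCPs will complete the SEEK Primary Care Provider Questionnaire (PCPQ) prior to the SEEK training". Under the implementation phase, "In month 5, practices in cohort 1 will be randomized to one of the two SEEK training strategies", and "At the end of training in month 8, PCPs will evaluate it". The Training paragraph says of the MOC arm that its four "one-hour webinars over 4 months enable collaborative learning and mentoring". For the second cohort the Timeline has "Month 11-15: Repeat above process with cohort 2 of healthcare systems and practices". Procedures starts SEEK itself in month 9 (A) and month 16 (B).

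On follow-up, Procedures says "Participants will be assessed at 12, 21 and 33 months post baseline regarding their thinking, feeling, behavior and experiences" and "At months 41 and 48, the observation period will end for cohorts 1 and 2". Under Phone Interviews, for office staff and parents, "interviews will be at 11, 20 and 32 months following start of the intervention". Practice leaders, PCPs and behavioral health professionals are interviewed around SEEK start and then 11 and 21 months later.

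The Aim 1 model in the Data Analysis Plan has a POST indicator (0 at baseline, 1 after training) and a POST by MOC term, with no MOC main effect. It therefore constrains the two arms to the same baseline mean. Recruitment places informed consent online, at the opening of the first survey.

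**The concern.** The plan gives two dates for one measurement. For cohort A, the month that Table 3 calls baseline is the month in which training ends, three months after allocation. By then the arms have received different things: MOC has had webinars and a quality-improvement cycle, IND has had the videos.

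This matters for the estimate. The constrained-baseline model attributes any arm difference at POST=0 to chance and adjusts the follow-up difference for it. That is right for a measure taken before training. If the difference is an early part of the training effect, the model subtracts some of the effect it is meant to estimate, and the POST by MOC coefficient is pulled towards zero. Comfort and competence on the PCPQ are the outcomes on which Table 4 bases the Aim 1a detectable effect of 0.42.

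**Working it through.** **1. Reproduce Table 3's follow-up months.** Inputs: Table 3 baselines (8, 15) and the intervals in Procedures (12, 21, 33 months).

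| | Baseline + 12, 21, 33 | Table 3 prints |
|---|---|---|
| Cohort A | 8+12=20, 8+21=29, 8+33=41 | 20, 29, 41 |
| Cohort B | 15+12=27, 15+21=36, 15+33=48 | 27, 30, 48 |

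Five of six agree. Months 8 and 15 are therefore the origin from which the plan counts, not a stray digit.

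**2. Place those months against training.** Cohort A is randomised in month 5 and training ends in month 8. Months 5 to 8 are four months, the stated length of the MOC webinars. Month 8 is the last training month. For cohort B the plan gives no training dates in the text. The window for recruitment, randomisation and training is months 11 to 15, so month 15 is its last month (an inference, where cohort A is explicit). Four months of training ending in month 15 would occupy months 12 to 15.

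**3. Move the baseline and keep the intervals.** With baseline at month 4 (A) and 11 (B), 12, 21 and 33 months later give 16, 25, 37 and 23, 32, 44. None is a Table 3 month for its cohort, and the last no longer falls at the end of observation (41 and 48). Counting from SEEK start instead gives 9+11=20, 9+20=29, 9+32=41 and 16+11=27, 16+20=36, 16+32=48. So a corrected baseline date needs a new anchor for the follow-ups.

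**4. Two cohort B cells.** Follow-up 2 is printed as month 30, but both counts give 36. Training is printed as by month 10, but that cohort's process starts in month 11. The lag between cohorts is 7 months for baseline, follow-up 1, follow-up 3 and SEEK start, but 1 month in these two cells (30−29 and 10−9). Each fits the 7-month lag if a final 6 was read as 0 (36 and 16).

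**5. Attenuation if Table 3 is followed.** The documents give neither the within-PCP correlation ρ nor the share f of the effect already present at month 8 or 15. Both are assumed here: ρ = 0.3 to 0.7, f = 25% or 50%. PCPs per practice: m = 275/48 = 5.73. Practice ICC implied by the 1.5-fold variance allowance in Sample Size Considerations: τ² = (1.5−1)/(5.73−1) = 0.106. With total variance 1 and the system effect left out, the model adjusts the practice-level follow-up difference by b times the baseline difference:

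b = [τ² + (ρ−τ²)/m] / [τ² + (1−τ²)/m]; expected estimate = 0.42 × (1 − f·b)

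The denominator is 0.106 + 0.894/5.73 = 0.262.

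| ρ | b | f = 0 | f = 25% | f = 50% |
|---|---|---|---|---|
| 0.3 | 0.140/0.262 = 0.53 | 0.42 | 0.364 | 0.308 |
| 0.5 | 0.175/0.262 = 0.67 | 0.42 | 0.350 | 0.280 |
| 0.7 | 0.209/0.262 = 0.80 | 0.42 | 0.336 | 0.252 |

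**The case against.** The strongest reply is that the intended order is clear. Procedures puts the PCPQ before training, in the phase described ahead of randomisation. Table 3 itself puts the baseline column before the training column and marks the PCPQ in both, which makes sense only as a before-and-after pair. The header is also shared with system demographics, the organisational scales and EHR screening rates, for several of which the month before SEEK starts is a natural baseline. All of this stands, and it is why the bias is conditional. It does not remove the conflict: the Timeline names Table 3 for timing, and the stated intervals work only from Table 3's months.

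Four stronger readings are tempting, and the documents do not support them.

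- **The Aim 1 result will be biased.** Only if staff schedule the PCPQ by Table 3. If they follow Procedures, it will not be.
- **Power drops by a stated amount.** Table 4's 0.42 at 80% power implies a standard error of 0.42/2.80 = 0.150, which is not that of the Aim 1 model. On the assumptions in step 5 that model gives 0.125, 0.110 and 0.089 for ρ = 0.3, 0.5 and 0.7. Setting the attenuated effects against 0.150 would mix two models, so no power figure is attached.
- **PCPs consent after allocation.** This follows only if Table 3's date governs the first survey. The available text does not say that consent must precede randomisation, but consent pages were removed from the public document and its Human Subjects section is not in the text at hand.
- **The cohort B cells are scheduling errors.** They may be misread digits in the public text, so they call for a check of the source and no more.

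**Conclusion.** The point holds as an internal contradiction about when the PCPQ baseline is taken. It is explicit for cohort A and inferred for cohort B, and it does not depend on any digit that could have been misread. The Procedures sentence on follow-up intervals is not wrong in itself; it agrees with Table 3 except in one cohort B cell. The fault lies in the baseline months on which it rests.

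The consequence ranges from none to an attenuated MOC effect of 0.34 to 0.36 SD (25% already present) or 0.25 to 0.31 SD (50% present) from a true 0.42 SD. Those ranges illustrate direction and rough size under assumed inputs and do not predict what the trial will find. The correction should be made because it is cheap and protects the assumption on which the Aim 1 model depends.

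**What to change.** - In Table 3 and Procedures, date the baseline PCPQ, with the consent taken at the first survey, before each cohort's randomisation: before month 5 for cohort A, and for cohort B before training starts, about month 12.
- Replace the post-baseline intervals for the surveys with 11, 20 and 32 months after SEEK start (months 9 and 16). This keeps 20, 29, 41 and 27, 36, 48 and ends with observation at months 41 and 48.
- Reconcile the interviews separately. Phone Interviews uses the 11, 20 and 32-month anchor only for office staff and parents. For practice leaders, PCPs and behavioral health professionals the last interview falls at 9+21=30 (A) and 16+21=37 (B), one month off the survey schedule.
- Check the source PDF for cohort B's follow-up 2 and training cells, and correct them only if they are printed as 30 and 10.

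The cost is wording, with no added survey. The practical burden is earlier readiness: the survey, online consent and IRB approval must be in place before month 5, whereas the Timeline spreads IRB approvals and computerising the protocol over months 1 to 8. Cohort B would have about one month (month 11) for consent, baseline and randomisation if four months of MOC training are to end by month 15.
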